4.3.1.1.2 Maximum Overall Intensity

Maximum overall intensity is derived from the daily intensities computed as described in [Section 4.3.1.1.1](#) and is calculated as the maximum of the daily intensities over the period considered.

4.3.1.1.3 Presence

Presence is derived from the maximum overall intensity over the time period considered:

- None: No presence
- Grade 1, Grade 2, or Grade 3: Presence
- Missing or Unknown: Missing presence

Participants with at least one non-missing presence for a specific endpoint will be included in the analysis. Conversely, those without a non-missing presence will not be included in the analysis of the endpoint.

The time period is displayed as D01-D04, D05-D08, D09 and later.

4.3.1.1.4 Time of Onset

Time of onset is derived from the daily intensities computed as described in [Section 4.3.1.1.1](#). It corresponds to the first day with intensity of Grade 1, Grade 2, or Grade 3.

Note: If a reaction is not continuous (ie, reaction occurs over two separate periods of time intervened by at least one daily intensity Missing or None) then the time of onset is the first day of the first presence.

Time of onset period is displayed as, D01-D04, D05-D08.

4.3.1.1.5 Number of Days of Presence During the Solicited Period

Number of days of occurrence over the period considered is derived from the daily intensities computed as described in [Section 4.3.1.1.1](#). It corresponds to the number of days with daily intensities of Grade 1, Grade 2, or Grade 3. Number of days of presence on the solicited period with a specified intensity may also be derived.

4.3.1.1.6 Overall Number of Days of Presence

If a reaction is ongoing at the end of the solicited period, then the overall number of days of presence is derived from the daily intensities and the end date of the reaction after the end of the solicited period. The overall number of days of presence is:

$(\text{End date} - \text{vaccination date}) + (\text{number of days of presence within the solicited period}) - \text{length of the solicited period} + 1$

If the end date is missing or incomplete (contains missing data), the overall number of days of presence will be considered as Missing.

4.3.1.1.7 Ongoing

Ongoing is derived from the last daily intensity of the solicited period computed as described in [Section 4.3.1.1.1](#) and the maximum intensity on the ongoing period. The investigator's ongoing flag is not used because the measurement would determine the ongoing status of the reaction.

- Ongoing: if the last daily intensity of the solicited period is at least Grade 1 and the maximum intensity on the ongoing period is at least Grade 1.
- Not ongoing: if the last daily intensity of the solicited period is None or the maximum intensity on the ongoing period is None.
- Missing: all other conditions (in this case, it won't be included in the denominator of the ongoing analysis in the safety tables).

4.3.1.2 Unsolicited AEs

4.3.1.2.1 Presence

An observation will be considered an event if it has at least a verbatim term and is not a Grade 0 intensity event.

Grade 0 events are not included in safety analysis but are included in separate listings.

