An unsolicited AE is an observed AE that does not fulfill the conditions of solicited reactions, ie, pre-listed in the CRF in terms of diagnosis and/or onset window post-vaccination. For example, varicella or a solicited term such as headache starting after the solicited observation period (headache starting on Day 10 post-vaccination in the case where headache occurring between the day of vaccination and the next 7 days is pre-listed in the protocol and CRF as a solicited reaction).

An unsolicited AR is an unsolicited AE that is considered related to study intervention. Unsolicited AEs includes both serious (SAEs) and non-serious unsolicited AEs.

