4.1.2 Time Period and Frequency for Collecting AE and SAE Information

Immediate Post-vaccination Observation Period

Participants will be kept under observation for 30 minutes after vaccination to ensure their safety. The post-vaccination observation should be documented in the source document and immediate events will be recorded at D01 in the eCRF.

Reactogenicity

Solicited injection site reactions will be collected from D01 to D08 after vaccination.

Solicited systemic reactions will be collected from D01 to D08 after vaccination.

The solicited injection site reactions and systemic reactions that are pre-listed in the diary cards and CRF, together with the intensity scales, are presented in [Table 4.1](#) and [Table 4.2](#).

Table 4.1: Solicited injection site reactions: terminology, definitions, and intensity scales

CRB term (MedDRA lowest level term [LLT])	Injection site pain	Injection site erythema	Injection site swelling
Diary card term	Pain	Redness	Swelling
Definition	Pain either present spontaneously or when the injection site is touched or injected limb is mobilized	Presence of a redness including the approximate point of needle entry	Swelling at or near the injection site Swelling or edema is caused by a fluid infiltration in tissue or cavity and, depending on the space available for the fluid to disperse, swelling may be either soft (typically) or firm (less typical) to touch and thus can be best described by looking at the size of the swelling

Intensity scale*	CRF: Grade 1: A type of adverse event that is usually transient and may require only minimal treatment or therapeutic intervention. The event does not generally interfere with usual activities of daily living. Grade 2: A type of adverse event that is usually alleviated with additional therapeutic intervention. The event interferes with usual activities of daily living, causing discomfort but poses no significant or permanent risk of harm to the research participant. Grade 3: A type of adverse event that interrupts usual activities of daily living, or significantly affects clinical status, or may require intensive therapeutic intervention. Diary card: Grade 1: No interference with usual activities Grade 2: Some interference with usual activities Grade 3: Significant; prevents usual activities	Grade 1: ≥ 25 to ≤ 50 mm Grade 2: ≥ 51 to ≤ 100 mm Grade 3: > 100 mm	Grade 1: ≥ 25 to ≤ 50 mm Grade 2: ≥ 51 to ≤ 100 mm Grade 3: > 100 mm
-------------------------	---	--	--

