4.3.1.2.2 Intensity

Intensity will be derived according to the following classification: None, Grade 1, Grade 2, Grade 3, or Missing

If the unsolicited AE is measurable and its preferred term is part of the list of solicited reactions, then the measurement is derived based upon and following the same rule of the intensity scales defined in the protocol for that measurable injection site or systemic reaction. Note the intensity could be considered as "None" (not a reaction) in the analysis despite being considered a reaction by the investigator (eg, swelling measurement > 0 mm but < 25 mm in adults)

Intensity for the other unsolicited AEs will correspond to the value reported in the CRF.

The maximum intensity corresponds to the highest intensity for a unique term.

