4.3.1.3.6 AEs Leading to Study Discontinuation

This information will be summarized as collected. A flag is available in the clinical database for all AEs in order to identify AEs leading to discontinuation before the end of active phase.

In general, the items that are counted are:

- Disposition table: A participant who, on the “Completion at End of Study” form question “What was the participant's status?” has “Adverse Event” checked.
- Safety overview table: A participant who has either on the “Completion at End of Study” form, question “What was the participant's status?” has “Adverse Event” checked or lists a solicited AE that has “Caused Study Termination” checked that is at least Grade 1 or an unsolicited AE that has “Caused Study Discontinuation” checked that is at least Grade 1 or missing and is within the time period indicated.
- SOC/PT table: A solicited AE that has “Caused Study Termination” checked that is at least Grade 1 or an unsolicited AE that has “Caused Study Discontinuation” checked that is at least Grade 1 or missing and is within the time period indicated.

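### The SAP's Grade 0 exclusion does not exempt serious AEs or AEs causing discontinuation, so a fever, erythema or swelling measured below the cut-off can drop out of those tables

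*SAP*

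**What the plan says.** SAP 4.3.1.2.1 defines what counts under unsolicited AEs: "An observation will be considered an event if it has at least a verbatim term and is not a Grade 0 intensity event". It continues: "Grade 0 events are not included in safety analysis but are included in separate listings". No exception follows.

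SAP 4.3.1.2.2 says where the grade comes from. The condition "If the unsolicited AE is measurable and its preferred term is part of the list of solicited reactions" sends the event to the solicited scale, and the grade is then derived from the measurement. For erythema and swelling that scale starts at "Grade 1: ≥ 25 to ≤ 50 mm" (SAP Table 4.1). For fever it starts at 38.0°C (SAP Table 4.2). A smaller value may be derived as None, which the note describes as "not a reaction) in the analysis despite being considered a reaction by the investigator". For everything else, "Intensity for the other unsolicited AEs will correspond to the value reported in the CRF".

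On scope, Protocol 10.3.1 states: "Unsolicited AEs includes both serious (SAEs) and non-serious unsolicited AEs". SAP 5.5.1.4 also treats SAEs as part of unsolicited AEs. The SAE subsection, 4.3.1.2.5, sits under the same parent heading as the Grade 0 rule. It identifies SAEs by the CRF seriousness box and covers every SAE during the study. SAP 5.4.2 and Protocol 9.4.2 promise tables of all SAEs with no grade condition.

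For discontinuations, SAP 4.3.1.3.6 counts an unsolicited AE with the discontinuation flag "checked that is at least Grade 1 or missing and is within the time period indicated". This applies in the SOC/PT table and in one of the two routes into the safety overview. The disposition table and the other overview route use the end-of-study form status, with no grade condition.

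**The concern.** Seriousness and intensity are different attributes, and Protocol 10.3.2 says so. An event is serious because of its outcome or the action it required, not because of its diameter or a temperature reading. The protocol endpoint is the presence of SAEs over the whole study, with no size condition. A derivation rule that removes events by measured size should not reach that endpoint, yet nothing in the SAP stops it.

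The rule is also asymmetric. An SAE with no intensity stays missing (SAP 5.5.1.3) and is kept. The same SAE with a small recorded measurement is removed. Injection-site events are related by convention (SAP 5.5.1.2), so a serious swelling lost this way would be a related SAE. In the discontinuation outputs, a participant could appear in the disposition table as having left for an adverse event while the SOC/PT table shows no such event.

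**Working it through.** The plan states no figure to reproduce. The check applies the rules to test values and then sizes the loss of one event.

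**Step 1. Which events can be derived as None.** Only a measurable unsolicited AE with a preferred term on the solicited list qualifies: fever, injection site erythema and injection site swelling.

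| Recorded value | Derived intensity | In tables under 4.3.1.2.1 |
|---|---|---|
| Fever 37.8°C | None | No |
| Fever 38.0°C | Grade 1 | Yes |
| Erythema or swelling 24 mm | None | No |
| Erythema or swelling 25 mm | Grade 1 | Yes |
| Not measured | Missing | Yes |

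Injection site pain, and any event coded to another preferred term, keeps its CRF grade. Under Protocol 10.3.1, a listed reaction starting in the D01 to D08 window is solicited, so the clearest case here is onset after D08.

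**Step 2. The rules by class of event.**
- *SAE with one of the three preferred terms and a value below the cut-off.* 4.3.1.2.1 says it is not an event and leaves it out; 4.3.1.2.5 and 5.4.2 include every SAE. No passage says which prevails.
- *AE of this kind that caused discontinuation.* It is absent from the SOC/PT table and from the AE-flag route of the overview. If the end-of-study form gives adverse event as the status, the participant still counts in the disposition table and the overview.
- *AESI.* The only one is anaphylaxis (SAP 4.1.4). It is not a solicited term, so its grade comes from the CRF and it cannot be derived as None.

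**Step 3. Size, for one assumed SAE.** The inputs are about 150 participants per group and 75 per age stratum (SAP 5.2), and exact Clopper-Pearson intervals (SAP 5.4.1). For x events in n, the lower limit is the 2.5% quantile of Beta(x, n − x + 1), set to 0 when x = 0. The upper limit is the 97.5% quantile of Beta(x + 1, n − x).

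| n | SAE kept | SAE dropped |
|---|---|---|
| 150 | 1/150 = 0.67% (0.02% to 3.66%) | 0/150 = 0% (0% to 2.43%) |
| 75 | 1/75 = 1.33% (0.03% to 7.21%) | 0/75 = 0% (0% to 4.80%) |

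**The case against.** The best defence is that the general subsections of 4.3.1.2 do not bind SAEs. Section 4.3.1.2.3 removes unsolicited AEs with onset after D31 from the analysis, yet 4.3.1.2.5 analyses SAEs from D32 to last contact. On this view the SAE subsection has its own inclusion rule, the seriousness box, and with 5.4.2 it already settles the matter. That is sound for timing, because 4.3.1.2.5 sets its own periods. It says nothing about grade, and it uses the word event, which 4.3.1.2.1 has just defined as excluding Grade 0. The conflict therefore remains. But it is a conflict: a reader might infer that the SAP deliberately excludes SAEs by size, and the promise of all SAEs does not support that.

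Other limits stand:
- The SAP never equates None with Grade 0. The link is inferred, although 4.3.1.2.2 has no other category below Grade 1.
- Protocol 10.3.3 asks for a diagnosis rather than signs where possible, and the site enters the highest diary temperature in the CRF (Protocol 10.3.5.1.1). Both make an SAE coded to plain fever, erythema or swelling with a small value unlikely.
- Excluded events stay in listings, and all analyses are descriptive.

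Three broader readings also fail. AESIs are not at risk. Injection-site events as a whole are not affected, only measured erythema and swelling. Discontinuations are not lost from every table.

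**Conclusion.** The point holds as an unresolved conflict with a narrow reach. Read literally, the Grade 0 rule removes from the SAE tables a serious fever, injection site erythema or injection site swelling with a recorded value below the cut-off, against the SAP's own commitment to report all SAEs. For discontinuations the grade filter is explicit, but only at event level in the SOC/PT table and in one overview route.

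The conclusion rests on reading None as Grade 0, and on 4.3.1.2.1 applying to SAEs because both documents class them as unsolicited AEs. The documents give no expected number of such events; few are likely. The percentages assume exactly one in an arm and show only what one lost case does: an arm with a single SAE would be tabulated as having none. That is enough to justify a clarification, and not a sign of wider trouble in the safety analysis.

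**What to change.** Add to SAP 4.3.1.2.1: *The Grade 0 exclusion does not apply to AEs flagged as serious or as causing study discontinuation; these are always included in the corresponding tables.*

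In 4.3.1.3.6, remove the grade condition for flagged unsolicited AEs from the SOC/PT rule and from the AE-flag route of the overview, so that both agree with the new sentence. The time-period condition can stay.

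Leave the intensity derivation in 4.3.1.2.2 as it is and show these events with their derived intensity, None. Substituting the investigator's grade would contradict the solicited-scale grading that Protocol 10.3.5.1.2 and SAP 4.1.2 require for measurable AEs on the solicited list. No AESI clause is needed.

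The cost is one added sentence, a matching edit to 4.3.1.3.6 and one programming condition. No data collection changes.

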4.3.1.2.2 Intensity

Intensity will be derived according to the following classification: None, Grade 1, Grade 2, Grade 3, or Missing

If the unsolicited AE is measurable and its preferred term is part of the list of solicited reactions, then the measurement is derived based upon and following the same rule of the intensity scales defined in the protocol for that measurable injection site or systemic reaction. Note the intensity could be considered as "None" (not a reaction) in the analysis despite being considered a reaction by the investigator (eg, swelling measurement > 0 mm but < 25 mm in adults)

Intensity for the other unsolicited AEs will correspond to the value reported in the CRF.

The maximum intensity corresponds to the highest intensity for a unique term.

4.3.1.2.3 Time of Onset

Time of onset is derived from the start date of the unsolicited AE and the date of the vaccination as described.

Time of Onset = start date of the unsolicited AE - date of the vaccination + 1

The time of onset is considered as missing only if one or both of the dates are missing or partially missing.

The unsolicited AEs will be analyzed "Within 30 days" after the vaccination, which corresponds to AEs with a time of onset between 1 and 31 days or missing. An AE with missing time of onset will be considered to have occurred just after the vaccination, so will be included in these tables.

Time of onset period is displayed as D01-D04, D05-D08, D09-D15, D16 or later, and Missing.

Note: Unsolicited AE that occurred before vaccination (null or negative time of onset) or with a time of onset higher than defined above will not be included in analysis but will be listed separately.

4.3.1.2.4 Duration

Duration is derived from the start and end dates of the unsolicited AE:

Duration = End date of unsolicited AE - start date of unsolicited AE + 1.

The duration should be considered as missing only if one or both of the start and end dates of the unsolicited AE is missing or partially missing.

4.3.1.2.5 SAEs

An event will be considered as a serious event if “Yes” is checked for “Serious” in the CRF.

SAEs will be analyzed throughout the study using at least the following periods:

- Within 30 days after the injection
- During the 6-month follow-up period (ie, from 31 days [from D32] after injection until the last participant contact)
- During the study (ie, all SAEs occurred during the study)

4.3.1.2.6 AESIs

An event will be considered as an AESI if “Yes” is checked for “Is the event an AESI?” in the CRF.

AESIs will be analyzed throughout the study using the following periods:

- Within 30 days after the injection
- During the 6-month follow-up period (ie, from 31 days [from D32] after injection until the last participant contact)
- During the study (ie, all AESIs occurred during the study)

4.3.1.3 Other Safety Endpoints

4.3.1.3.1 Pregnancy

This information will not be included in the analysis but will be listed separately. No derivation or imputation will be done.

4.3.1.3.2 Action Taken

This information will be summarized as collected, including missing observations. No derivation or imputation will be done.

4.3.1.3.3 Seriousness

This information will be summarized as collected. No derivation or imputation will be done.

4.3.1.3.4 Outcome

This information will be summarized as collected. No derivation or imputation will be done.

4.3.1.3.5 Causal Relationship

This information will be summarized as collected in the field “Relationship to Investigational Product”. Missing causal relationship will be handled as described in [Section 5.5.1.2](#). Relationship to study procedure for SAE is only presented in the listings.

4.3.1.3.6 AEs Leading to Study Discontinuation

This information will be summarized as collected. A flag is available in the clinical database for all AEs in order to identify AEs leading to discontinuation before the end of active phase.

In general, the items that are counted are:

- Disposition table: A participant who, on the “Completion at End of Study” form question “What was the participant's status?” has “Adverse Event” checked.
- Safety overview table: A participant who has either on the “Completion at End of Study” form, question “What was the participant's status?” has “Adverse Event” checked or lists a solicited AE that has “Caused Study Termination” checked that is at least Grade 1 or an unsolicited AE that has “Caused Study Discontinuation” checked that is at least Grade 1 or missing and is within the time period indicated.
- SOC/PT table: A solicited AE that has “Caused Study Termination” checked that is at least Grade 1 or an unsolicited AE that has “Caused Study Discontinuation” checked that is at least Grade 1 or missing and is within the time period indicated.

4.3.2 Immunogenicity

4.3.2.1 Computed Values for Analysis

In order to appropriately manage extreme values (< LLOQ and \geq ULOQ (lower limit of quantitation and upper limit of quantitation, respectively)) for analysis purposes of Geometric Mean Titer (GMTs), Geometric Mean Concentration (GMCs), and thresholds the following computational rules will be applied to the values provided in the clinical database:

- If a value is < LLOQ, then the computed value is LLOQ/2
- If a value is between \geq LLOQ and < ULOQ, then the computed value is the value
- If a value is \geq ULOQ, then the computed value is ULOQ

4.3.2.2 Thresholds

Generally, if the computed value is $\geq x$, then the derived indicator will be "Yes" for that test, otherwise indicator will be "No".

Note: If the computed value is missing, indicator will be missing.

The thresholds are summarized in the table below:

Table 4.3: Immunogenicity thresholds of interest

Endpoints	D01 (V01)	D31 (V02)
Pneumococcal serotype specific functional Ab (OPA)	\geq LLOQ	\geq LLOQ
Pneumococcal serotype specific binding IgG	\geq LLOQ	\geq LLOQ

4.3.2.3 Fold-rise

The derived endpoint fold-rise is driven by both baseline and post-baseline computed values. The following algorithm will be used to minimize the numerator and maximize the denominator.

- If the baseline computed value is $<$ LLOQ and the post-baseline computed value is $<$ LLOQ then the fold-rise is 1
- If the baseline computed value is \geq LLOQ and the post-baseline computed value is \geq LLOQ then the fold-rise is post-baseline computed value / baseline computed value
- If the baseline computed value is \geq LLOQ and the post-baseline computed value is $<$ LLOQ then the fold-rise is $(LLOQ/2) / \text{baseline computed value}$
- If the baseline computed value is $<$ LLOQ and the post-baseline computed value is \geq LLOQ then the fold-rise is post-baseline computed value /LLOQ

If the computed value is $\geq X$ -fold rises, then the derived $\geq X$ fold rises indicator will be "Yes" for that test, otherwise $\geq X$ -fold rises will be "No".

Note: If baseline or post-baseline is missing, then fold-rise is missing.

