9.4.1 General Considerations

All analyses will be descriptive.

For immunogenicity data, assuming that log10 transformation of the titers / concentrations and titers / concentrations ratio follows a normal distribution, first, the mean and 95% confidence intervals (CIs) will be calculated on log10 (titers / concentrations; titers / concentrations ratio) using the usual calculation for normal distribution, then antilog transformations will be applied to the results of calculations, to compute geometric mean titers / concentrations (GMTs / GMCs) and geometric mean of the individual titer / concentration ratios (GMTRs / GMCRs) and their 95% CIs.

The 95% CIs of ratio of GMTs / GMCs between 2 groups will be computed from the difference of log 10 transformed means of titers/concentrations using normal approximation.

The 95% CIs of point estimates will be calculated using the exact binomial distribution (Clopper-Pearson method (29)) for proportions.

Generally, no replacement of missing data will be done.

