9.4.3 Immunogenicity Analyses

All immunogenicity analyses will be performed on the PPAS and presented by group and age group. Additional immunogenicity analyses will be performed on the FAS.

The point estimates and their 95% CI of at least the following parameters will be presented before and 1-month post-vaccination for each pneumococcal serotype specific OPA titers and IgG concentrations:

- GMT/GMC of serotype specific titers/concentrations
- GM of titers/ concentrations ratio (post- / pre-vaccination)

Differences in terms of ratio of GMTs/GMCs between 2 groups (ie, any SP0202 formulations and Prevnar 13 or Pneumovax 23) post-vaccination will be presented.

Reverse cumulative distribution curves (RCDCs) of individual concentrations/titers will be presented for all serotypes at pre and post-vaccination.

Missing data will not be imputed. No test or search for outliers will be performed.

For the calculation of GMTs / GMCs and percentage above cut-offs, any pre-vaccination or post-vaccination value reported as < LLOQ will be converted to a value of 0.5 LLOQ.

For the calculation of GMTR / GMCR, any pre-vaccination value reported as < LLOQ will be converted to LLOQ, and any post-vaccination value reported as < LLOQ will be converted to a titer of 0.5 LLOQ when only either the numerator or the denominator is < LLOQ. If both

numerator and denominator are < LLOQ, then both will be converted in the same way so that the increase is defined as 1.

Any value reported as > ULOQ (upper limit of quantitation) will be converted to ULOQ.

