5.4 Statistical Analyses

5.4.1 General Considerations

The statistical analyses will be performed under the responsibility of the Sponsor's Biostatistics platform using SAS® Version 9.4 software or later.

The results of the statistical analysis will be available in the final clinical study report (CSR).

For descriptive purposes, the following statistics will be presented:

Table 5.1: Descriptive statistics produced

Baseline characteristics and follow-up description	Categorical data	Number of participants. Percentage of participants.
	Continuous data	Mean, standard deviation, median, quartiles, minimum, and maximum.
Clinical safety results	Categorical data	Solicited: Number and percentage (95% CIs) of participants. Unsolicited: Number and percentage (95% CIs) of participants, and number of events.
Immunogenicity results	Categorical data (threshold, fold-rise)	Number and percentage (95% CIs) of participants.
	Continuous data (titer / data)	Log10: Mean and standard deviation. Anti-Log10 (work on Log10 distribution, and anti-Log10 applied): Geometric mean, 95% CI of the geometric mean, quartiles, minimum, and maximum. Graphical representation by Reverse Cumulative Distribution Curve (RCDC). Boxplots and Forest plots.

The CI for the single proportion will be calculated using the exact binomial method (Clopper-Pearson method, quoted by Newcombe (2)), ie, using the inverse of the beta integral with SAS.

For immunogenicity results, assuming that \log_{10} transformation of the titers / concentrations follows a normal distribution, at first, the mean and the 95% CI will be calculated on \log_{10} (titers / data) using the usual calculation for normal distribution (using Student's t distribution with $n-1$ degree of freedom), then antilog transformations will be applied to the results of calculations, in order to provide geometric means (GMs) and their 95% CI.

CIs of ratio of GMTs / GMCs between 2 groups will be computed from the difference in means of \log_{10} transformed titers/concentrations between 2 groups with normal approximation.

Disposition, demographics, medical history, and concomitant medications data will be summarized using counts and percentages.

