5.4.3 Immunogenicity Analyses

The immunogenicity analyses will be performed first on the PPAS and then on the FAS.

The point estimates and their 95% CI of the following parameters will be presented by group for all participants and by age group before and one month post-vaccination for each pneumococcal serotype specific OPA titers and IgG concentrations:

- GMT/GMC of serotype specific titers/concentrations.
- GMT/GMC ratio (post/pre-vaccination).

In addition, the following analyses will be presented:

- Differences in terms of ratio of GMTs/GMCs between 2 groups (for instance, any SP0202 formulations and Prevnar 13 or Pneumovax 23) and 95% CI at 1-month post-vaccination on all participants and by age group.
- Percentages of participants with titers/concentrations above certain thresholds and achieving several X-fold from pre to post-vaccination.
- Several graphical representations (in a log10 scale) will be used for all serotypes by group for all participants and by age group:
 - RCDCs of individual OPA titers and IgG concentrations at pre and 1-month post-vaccination.
 - Forest plots of GMTs or GMCs at pre and 1-month post-vaccination.
 - Forest plots of GMT/GMC ratio between groups at 1-month post-vaccination.
 - Boxplots of the OPA titers and IgG concentrations at pre and 1-month post-vaccination.

Table 5.2: Summary of statistical analyses for immunogenicity analysis

Endpoint	Visit and Age group	Description
Serotype-specific pneumococcal OPA titer for each of the 21 serotypes	V01 and V02 - all participants	OPA GMT and 95% CI, corresponding Forest Plot
	V01 and V02 - 50-64 years	
	V01 and V02 - 65-84 years	
	V02/V01 - all participants	OPA GMT ratio (post/pre) and 95% CI
	V02/V01 - 50-64 years	
	V02/V01 - 65-84 years	
	V02/V01 - all participants	Percentage of participants with titers at V02 \geq 2/4/8/16-fold rise over V01 and 95% CI and <LLOQ at V01 to \geq LLOQ at V02
	V02/V01 - 50-64 years	
	V02/V01 - 65-84 years	
	V02 - all participants	OPA GMT ratio and 95% CI and corresponding Forest Plot between:
	V02 - 50-64 years	
 - each SP0202 formulation (ie, SP0202-VI/SP0202-IIb, SP0202-VII/SP0202-IIb, SP0202-VII/SP0202-VI) - any SP0202 group and Prevnar 13 or Pneumovax 23 (ie, SP0202-IIb/Prevnar 13, SP0202-VI/Prevnar 13, SP0202-VII/Prevnar 13; SP0202-IIb/Pneumovax 23, SP0202-VI/Pneumovax 23, SP0202-VII/Pneumovax 23)
	V02 - 65-84 years	
	V01 and V02 - all participants	OPA titer RCDC
	V01 and V02 - 50-64 years	

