5.4.4 Other analyses

COVID-19

Impact of COVID-19 pandemic on study conduct and disposition of participants impacted by COVID-19 pandemic situation will be summarized in tables on all participants and by age group and listed in Appendix 16 of the CSR.

If more than 10% of randomized participants are impacted by COVID-19, and still evaluable for immunogenicity/safety timepoints, additional analyses in impacted/non-impacted participants will be done on main immunogenicity and safety endpoints.

In addition, in case the 2019-nCOV serostatus is determined for the participants (see Section 4.2 of the protocol), at minimum, results will be presented for tested participants.

Subgroup Immunogenicity analyses

Additional analyses will be done according to gender (two categories: Male, Female), race (two categories: the modality[ies] the most represented versus the pool of the other modalities) and IgG/OPA baseline LLOQ status (ie, <LLOQ or \geq LLOQ) on the main parameters:

- GMT/GMC of serotype specific titers/concentrations
- GMT/GMC ratio (post/pre-vaccination)

Baseline adjusted Immunogenicity analyses

In addition to GMT/GMCs ratio between groups, GMTs/GMCs ratio will be computed using constrained Longitudinal Data Analysis (cLDA) model (3).

CLDA will be used to take into account baseline titer/concentration in the model. This approach assumes that the baseline mean values are equal between all groups (reasonable assumption because of the randomization).

Correlation heatmap Immunogenicity analyses

Correlation heatmaps will be plotted for both serotype specific IgG concentrations and serotype specific OPA titers at post-vaccination using the Spearman's correlation matrix across serotypes. One figure for each group separately will be plotted, and one figure pooling the three SP0202 groups will be plotted as well.

All the 'Other analyses' will be conducted in the FAS and provided in Appendix 15 of the CSR.

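### Does dividing by LLOQ, while the GMTs use LLOQ/2, make the post/pre ratio wrong?

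*SAP*

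**What the plan says.** SAP 4.3.2.1 covers GMTs, GMCs and thresholds: "If a value is < LLOQ, then the computed value is LLOQ/2", at either visit.

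SAP 4.3.2.3 gives four branches for the fold-rise and says that they are built to keep the numerator small and the denominator large. When the baseline is below LLOQ and the post-vaccination value is not, "then the fold-rise is post-baseline computed value /LLOQ".

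Protocol 9.4.3 has the same rule and ties it to the endpoint by name: "For the calculation of GMTR / GMCR, any pre-vaccination value reported as < LLOQ will be converted to LLOQ". Protocol 9.4.1 defines that endpoint as the "geometric mean of the individual titer / concentration ratios (GMTRs / GMCRs").

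The SAP is looser in its output list. Table 5.2 calls the result "OPA GMT ratio (post/pre) and 95% CI", and Table 5.1 mentions fold-rise only under "Categorical data (threshold, fold-rise"). SAP 5.5.2 sends the reader to both 4.3.2.1 and 4.3.2.3 for LLOQ handling.

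**The concern.** The SAP label reads as the post-vaccination GMT divided by the pre-vaccination GMT. A reader who divides the two tabulated GMTs will get a larger number than the one printed. The gap comes from the assay limit, and it varies by serotype and arm with the share of participants who cross LLOQ. It is widest in the planned subgroup by "IgG/OPA baseline LLOQ status": the factor is 1 in the stratum at or above LLOQ and nears one half in the other if almost everyone becomes quantifiable.

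The post/pre ratios are two of the four immunogenicity endpoints, reported for 21 serotypes in five arms. No hypothesis is tested, so no test needs a conservative rule. It is natural to ask why the ratio is not built from the same LLOQ/2 values as the GMTs.

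**Working it through.** The documents state no figure on this point, so there is nothing to reproduce. The check is algebra, followed by an illustration.

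**Identity.** Let B and P be the computed values under SAP 4.3.2.1 and FR the fold-rise under 4.3.2.3. Compare FR with P/B:

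| Baseline | Post | FR | P/B | FR ÷ (P/B) |
|---|---|---|---|---|
| <LLOQ | <LLOQ | 1 | (LLOQ/2)/(LLOQ/2) = 1 | 1 |
| ≥LLOQ | ≥LLOQ | P/B | P/B | 1 |
| ≥LLOQ | <LLOQ | (LLOQ/2)/B | (LLOQ/2)/B | 1 |
| <LLOQ | ≥LLOQ | P/LLOQ | P/(LLOQ/2) | 1/2 |

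Averaging logs over complete pairs gives

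GM(FR) = [GM(P)/GM(B)] × 2^(-p01), a log10 shift of -0.301 × p01.

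The factor is 0.933 at p01 = 0.10, 0.841 at 0.25, 0.707 at 0.50 and 0.500 at 1. In simulated data sets of 128 pairs the identity held exactly: for p01 = 0.570, 4.048 × 2^(-0.570) = 2.726, and the directly computed GM(FR) was 2.726.

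**Size under assumptions.** The share below LLOQ, the SD and the pre/post correlation are all assumed. With log10 SD 0.6, correlation 0.5, a true 10-fold rise and 2,000,000 simulated pairs per row:

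| Baselines <LLOQ | p01 | Post GMT / pre GMT | GM(FR) | Shift, 0.301 × p01 | 95% CI half-width, n = 128 |
|---|---|---|---|---|---|
| 20% | 0.195 | 9.85 | 8.60 | 0.059 | 0.099 |
| 30% | 0.289 | 9.45 | 7.74 | 0.087 | 0.097 |
| 50% | 0.458 | 8.10 | 5.90 | 0.138 | 0.093 |

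The shift first exceeds the half-width at about 25% to 60% of baselines below LLOQ, across SD 0.6 to 0.9 and correlation 0.5 to 0.8. The share with at least a 4-fold rise is 72% against 74% in the 20% row, and 62% against 71% in the 50% row. In the baseline-below-LLOQ stratum of the 50% row, the ratio is 6.1 against 11.4. With no true change, GM(FR) is 0.89 to 0.98 instead of 1.00 (20% to 80% below LLOQ, correlation 0.5 to 0.95).

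**What LLOQ/2 would do instead.** Anyone crossing has P ≥ LLOQ, so P/(LLOQ/2) ≥ 2. Every crossing would count as at least a 2-fold rise, even from just under the limit to just on it. Under the plan's rule the same crossing gives at least 1, a lower bound on the true rise. The ≥2/4/8/16-fold indicators are derived inside 4.3.2.3 from this one algorithm, so at present they and the mean ratio share a definition.

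**Would the tables then agree?** Not necessarily. The fold-rise needs both visits, whereas the FAS and PPAS require only a valid post-vaccination result. With a few baselines missing and GMTs taken on all available samples, the identity was only approximate (2.78 against 2.69 in one data set). The same mismatch would remain with LLOQ/2 throughout.

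**The case for a change.** The best case for a change has three parts.

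- **Labelling.** Read alone, the SAP does not say in 5.4.3 that the post/pre ratio uses 4.3.2.3. It also uses the name GMT ratio for the between-group quotient, which rests on LLOQ/2. This stands as an editorial point. It leaves little doubt about the calculation: 4.3.2.1 limits itself to GMTs, GMCs and thresholds, 5.5.2 cites 4.3.2.3, and the protocol names the endpoint when it states the rule. The Table 5.1 entry fits the fold-rise indicators and does not rule out a mean.

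- **Uneven attenuation between arms.** Prevnar 13 lacks eight of the 21 serotypes. At 50% below LLOQ (SD 0.6, correlation 0.5), p01 is 0.458 with a 10-fold rise and 0.166 with none. The factors are 0.73 and 0.89, so a contrast of fold-rises shrinks by about 18% (0.73/0.89 = 0.82). That is correct arithmetic. However, the plan compares arms through V02 GMT/GMC ratios and cLDA, and it names Pneumovax 23 as the reference for those eight serotypes. Among arms that respond, p01 is close to the baseline share below LLOQ (0.195 of 0.20, 0.289 of 0.30), and randomization balances that share in expectation.

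- **Closeness to the truth.** In the simulated rises the LLOQ/2 version is nearer to 10-fold. That is so, but it depends on the assumed spread of baselines below the limit, where the assay gives no value. LLOQ/2 also falls short in all three rows.

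The remedy is not free either. Making LLOQ/2 primary departs from protocol 9.4.3. It would also either split the definition used for the mean from that used for the indicators, or change both.

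**Conclusion.** No change is needed. The plan's post/pre ratio is a deliberately conservative geometric mean of individual fold-rises, prespecified alike in protocol and SAP. In complete pairs it lies below the quotient of the GMTs by the exact factor 2^(-p01), between 1 and 0.5. Where in that range it falls cannot be told from the documents; every figure beyond the identity rests on assumed shares, SDs and correlations.

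Replacing the rule would exchange one substitution convention for another, a fair trade-off with arguments on both sides. The largest subgroup gap lies in a supplementary FAS analysis for a CSR appendix. Table 5.2 already plans the percentage going from below LLOQ to quantifiable ("2/4/8/16-fold rise over V01 and 95% CI and <LLOQ at V01 to" LLOQ or above at V02), so a reader can recover the quotient of GMTs in complete pairs. Calling the output a geometric mean fold-rise under 4.3.2.3 would be clearer, but that is wording an analyst can supply in the table shells, and it alters no estimate or interval.
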